Objectives	
1. To detect a change in the PI3Kgamma regulated gene expression signature of immune suppression.2. To detect change in myeloid, T cell composition and immune activation markers by IHC as well as TCR sequencing3. To determine safety and tolerability of IPI-549 and change in tumor size in patients with locally advanced HNSCC.
Number of Subjects	15
Diagnosis and Main Inclusion Criteria	Eligible patients (n=15) with pathologically confirmed locally advanced, previously untreated HNSCC that is amenable to surgical resection.
Study Product(s), Dose, Route, Regimen	IPI-549, 40 mg QD PO* *Final dose based on ongoing Phase 1 study [NCT02637531]
Duration of administration	At least 14 days
Reference therapy	N/A
Statistical Methodology	We anticipate enrolling 15 subjects. Within subject change from the post-treatment to the pre-treatment sample in the immune activation signature will be the primary endpoint. We will test the hypothesis of an increase in this signature using a one sided paired t-test at 5% significance level. With 15 subjects we have 80% power to detect a difference in the mean signature equal to 0.68 standard deviations. A safety stopping rule will halt the study if at any time 3 or more subjects have observed progression prior to surgery.

SCHEDULE OF EVENTS

Procedure	Screen/ Baseline (≤ 28 days)	Window of Opportunity Week 1 Day 1 (±3 days)	Pre-Surgery ¹⁰ Week 2 Day 14 (±3 days)	Follow-up
Informed Consent	Within 28 days			Approximately 30 days (±7 days)after last dose of study drug
Eligibility	X			
Medical History	X			
Demographics	X			
Concomitant Medications Assessment	X	X	X	X ⁹
Adverse Event Assessment		X	X	X ⁹
Physical Exam ¹	X	X	X	X
Vital Signs and Height	X		X	X
ECOG PS	X		X	X
CBC with Diff ²	Within 7 days	X	X	X
CMP ³	Within 7 days	X	X	X
Pregnancy test ⁴	Within 72 hours			
HIV (as clinically indicated)	X (Within 7 days)			
HEP B & C (as clinically indicated)	X (Within 7 days)			
ECG (12-lead)	X			
Tumor tissue collection ⁵	X		X ¹¹	
Blood Collection for Correlative studies ⁶	X(Within 7 days)		X	
MRI or CT (neck & chest)				X ⁷
IPI-549 administration ⁸		X		
Safety follow up				X

IPI-549 is 14 days in length with the last administration within 24 hours of surgery.

1. Full physical exam at baseline; targeted physical exam at other time points.
2. CBC with Diff: Complete blood count with differential.
3. CMP: Comprehensive metabolic panel (bicarbonate, calcium, chloride, creatinine, glucose, potassium, sodium BUN, albumin, bilirubin total, alkaline phosphatase, total protein, ALT, AST).
4. Pregnancy test for females of child-bearing potential only.
5. Tumor tissue collection: See Section 6.1.8 for specifications.
6. Blood for correlative studies should be collected at the same time blood is drawn for CBC and CMP if possible. 40 mL blood to be collected at baseline; 30 mL blood to be collected at pre-surgery visits. See Section 6.1.8.
7. Scans will be performed when clinically indicated.
8. IPI-549 administration (Section 5.2): administered PO 40 mg QD until 24 hours prior to date when surgery is performed. Not allowed less than 24 hours of surgery.
9. In Follow-Up period, concomitant medications will be collected at Safety Follow-Up visit (approximately 30 (+7) days after the last dose of study drug) and for SADs. During this period, adverse events will be collected at Safety Follow-Up and SAEs until 90 days after last dose of study drug.
10. Surgery is to be performed no later than 48 hours after last dose of therapy. Therapy should continue until the day before surgery.
11. Tumor tissue collection to occur during surgery.

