5.2 Treatment Dosage and Administration

IPI-549 will be administered 40 mg orally over a 14 day cycle. Dose of IPI-549 will be determined based on observed toxicity in ongoing Infinity clinical trial (NCT02637531). IPI-549 should be self-administered orally (approximately every 24 hours). IPI-549 should be swallowed whole with a glass of water (approximately 8 ounces or 240 mL). Subjects must avoid grapefruit and grapefruit juice while on study drug. Subjects should be advised to avoid food and liquids other than water from 2 hours prior to dosing until 1 hour after dosing.

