5.3 Duration of Study Treatment

IPI-549 for 2 weeks prior to surgical resection. Subjects will be monitored continuously for toxicity while on study therapy. Toxicity will be assessed using the NCI-CTCAE, v. 5.0 or higher. There will be no dose modification allowed on study. Missed doses should be recorded on the pill diary. Any grade 3 toxicity will result in discontinuation of IPI-549. If at any time 3 or more subjects have observed progression prior to the start of definitive treatment the study will be halted.

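### The note under the Schedule of Events puts the last IPI-549 dose within 24 hours of surgery, where footnote 8 prohibits dosing

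*Combined protocol and SAP*

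**What the plan says.** Three places in the Schedule of Events govern the last dose before surgery.

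- The note directly under the table: "IPI-549 is 14 days in length with the last administration within 24 hours of surgery".
- Footnote 8, attached to the IPI-549 row: "administered PO 40 mg QD until 24 hours prior to date when surgery is performed", followed by the prohibition "Not allowed less than 24 hours of surgery".
- Footnote 10, attached to the pre-surgery visit: "Surgery is to be performed no later than 48 hours after last dose of therapy", followed by "Therapy should continue until the day before surgery".

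The body of the protocol does not choose between them. Section 5.2 has patients dose themselves about once every 24 hours and sets no clock time. Its fasting instruction, to "avoid food and liquids other than water from 2 hours prior to dosing until 1 hour after dosing", can be met at any hour. Section 5.3 gives a two-week course before resection and adds "Missed doses should be recorded on the pill diary". Section 9.1 limits the efficacy population to subjects who received two weeks of study drug and replaces the others.

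**The concern.** The note and footnote 8 give opposite limits for the same interval. Whoever instructs the patient from the note will aim for a last dose in the final 24 hours, which is the period footnote 8 closes. The protocol treats that bar as a prohibition and not a preference, so following one line of the schedule produces a deviation from another, in a patient about to have cancer surgery.

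Footnote 10 adds a smaller difficulty. It sets the last dose by calendar day, while footnote 8 sets it by hours. For a patient who doses later in the day than the operation begins, the two differ, and the text does not say which governs.

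A dose left out to respect the 24 h bar also needs a stated status. Section 5.3 would have it entered as a missed dose, and Section 9.1 does not say whether the subject still counts as having had two weeks of drug.

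**Working it through.** The plan's one power figure does not enter this point. It reproduces: one-sided paired t-test at 5%, 15 subjects, effect 0.68 SD, noncentral t with 14 degrees of freedom and noncentrality 0.68 × √15 = 2.63, giving power 0.805 against the stated 80%.

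**Step 1: limits on the gap.** Let *g* be the hours from last dose to start of surgery.

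| Source | Limit on *g* |
|---|---|
| Note under the table | *g* ≤ 24 |
| Footnote 8, prohibition | *g* ≥ 24 |
| Footnote 10, upper limit | *g* ≤ 48 |

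- Note and footnote 8 together: *g* = 24 exactly.
- Footnotes 8 and 10 together: 24 ≤ *g* ≤ 48.

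Without the note, the remaining two limits form a workable window.

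**Step 2: the calendar-day rule.** Let the day-before dose be at clock hour *d* and surgery at clock hour *s*. Then *g* = 24 − *d* + *s*, so *g* ≥ 24 only when *d* ≤ *s*. The documents give no clock times; those below are assumed for illustration.

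| Day-before dose | Surgery start | *g* (h) | Footnote 8 | Note |
|---|---|---|---|---|
| 20:00 | 08:00 | 24 − 20 + 8 = 12 | broken | met |
| 09:00 | 07:30 | 24 − 9 + 7.5 = 22.5 | broken | met |
| 07:00 | 07:30 | 24 − 7 + 7.5 = 24.5 | met | broken |
| 08:00 | 10:00 | 24 − 8 + 10 = 26 | met | broken |

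Every row satisfies both sentences of footnote 10. No row satisfies the note and footnote 8 together.

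**Step 3: does omitting the offending dose stay within 48 h?** If the day-before dose would fall at *g* < 24, the previous dose on an exact 24 h schedule is at *g* + 24, which lies between 24 and 48. In the 09:00 and 07:30 case it is 22.5 + 24 = 46.5 h. Section 5.2 requires only approximate 24 h spacing, so a dose drifting by an hour could push this slightly past 48 h when *g* is close to 24 (for example 23.5 + 25 = 48.5 h). The same latitude allows the previous dose to be taken a little later that day.

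**Step 4: footnote 8's first sentence.** It counts 24 h back from the date of surgery. Counted from midnight at the start of that date, this would exclude nearly every day-before dose and collide with footnote 10. The next sentence of footnote 8 counts from surgery itself, so this is probably loose wording, but it should be tidied with the rest.

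**The case against.** The best reply is that the note is one loose sentence. Footnotes 8 and 10 carry the working rule and can be met together: last dose 24 to 48 h before surgery, on the preceding day when the clock allows. A careful reader applies both, and an explicit prohibition takes precedence over a general stopping day. Much of this stands. A reader might infer that footnotes 8 and 10 contradict each other; they do not. Footnote 10 is less specific and needs to be made subject to the bar. The reply does not rescue the note, which states a limit opposite to a prohibition, with nothing elsewhere to say that it yields.

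A reader might also infer that respecting the bar costs subjects their place in the efficacy population. With 09:00 dosing from Day 1 and surgery at 07:30 on Day 15, omitting the Day 14 dose leaves 13 doses. But Section 9.1 speaks of two weeks of drug, not 14 doses, and Section 5.3 only asks that missed doses be recorded. Exclusion would rest on a threshold the plan does not contain. What remains is a gap that one sentence can close.

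Finally, the clock times are assumed, and the examples show that a breach can occur, not how often it would.

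**Conclusion.** The contradiction is in the current text and should be corrected. The note and footnote 8 share a single value, 24 h, and any other time that obeys the note breaks the prohibition. That result needs no assumption beyond reading the two limits as written. The footnote 10 point is secondary: it arises only when the day-before dose is taken later in the day than surgery begins.

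A reader might go further and suppose that the variable dose-to-surgery gap biases the signature comparison. The documents do not support that. They give no reason for the 24 h bar and no evidence that a gap of, say, 22 h rather than 46 h changes the signature. The endpoint, the test, the 15 subjects and the stated power are untouched. This is an error in a conduct and safety instruction, inexpensive to remove, and worth removing because it governs dosing just before an operation.

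**What to change.** - Replace the note with: *The last dose is taken at least 24 h and no more than 48 h before the scheduled start of surgery.* This is the range footnotes 8 and 10 already share, so it adds no new constraint.
- Reword footnote 8 to count from the scheduled start of surgery and not from its date.
- Reword footnote 10: *Daily dosing continues up to the day before surgery; that day's dose is omitted if it would fall less than 24 h before the scheduled start.*
- Add to Section 9.1 that a dose omitted for this reason does not by itself make a subject non-evaluable or require replacement.
- Record the time of the last dose and the start time of surgery, if the CRF does not already capture them.

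The cost is a few wording changes and at most two CRF fields, with no added patient procedure and no change to the analysis. A minimum of 14 doses, or a rule moving surgery to Day 16, is not needed: either would tie the date of definitive cancer surgery to a dose count that the plan does not require.

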3.3 Endpoints

We hypothesize that mRNA signatures of immune response will be increased in IPI-549-treated HNSCC patients. For the efficacy endpoints, RECISTv1.1 will be used.

Primary Endpoints

We hypothesize that the 5-gene mRNA immune response signature from Kaneda et al. [2] will increase with treatment.

Specifically, the signature is: $s = IL12A + IL12B + IFNG + CD8A - IL6$, measured by RNA expression levels from a custom Nanostring Immune Profiling panel.

Secondary Endpoints

1. Adverse events related to IPI-549 (description, grade [CTCAE v5.0], and seriousness).
2. T cell receptor (TCR) sequencing from blood obtained at baseline, surgery, end of treatment or at time of disease progression.
3. Comparison of pre- vs. post-treatment tumor tissue for CD8 expression by immunohistochemistry
4. Comparison of pre- vs. post-treatment peripheral cytokines and immune cells.

We hypothesize that the 42-mRNA signature of PI3K γ [2] will increase with treatment. Gene expression will be assessed by Nanostring custom panel.

Specifically, the signature is comprised of the sum of 21 immune response and T-cell activation genes, plus the sum of 10 antigen presentation genes, minus the sum of 11 immune suppression genes [2] listed below.

Gene lists for the PI3Kgamma activation signature are:

- *Immune suppression genes:* *PDGFA PDGFB HBEGF PLA2U F3 IFIT1 CD276 IL6 CCL7 CCL4 ID2*
- *Immune response, T cell activation genes:* *IER3 ADORA2A CCR7 RASGRP1 CXCR3 CX3CR1 IL12B IL12A CD4 CD8A CD8B GZMA GZMK GZMH GZMM IFNG CD28, LAT LAG3 ZBP1 BTLA MALT1*

- *Antigen presentation genes:*
HLA_DMA HLA_DMB HLA_DRB5 HLA_DOB CIITA 0 HLA_DQA2 HLA_DRA HLA_DOA HLA_DQB2 CD74.

Exploratory endpoints

Three IHC panels to assess myeloid and T cell content and activation states, each panel is expected to increase with treatment

- Lymphoid panel: PD-1, CD3, RORgt, CD56, CD8, Tbet, GATA3, FoxP3 PD-L1, CD20, CD45, p16
- Myeloid panel: Tryptase, CD68, CSF1R, DC-SIGN, CD66b, CD83, CD163, MHCII, PD-L1, CD3/20/56, CD45, p16
- T cell activation panel: CD3, CD4, CD8, IDO, Tbet, CD68, PD-1, Eomes, Ki67, Granzyme B, CD45

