6.1.6 Clinical Laboratory Tests

Blood chemistry, hematology, and β hCG pregnancy tests will be administered throughout the study to monitor safety.

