7.0 ADVERSE EVENTS

An adverse event (AE) is any untoward medical occurrence in a patient receiving study treatment and which does not necessarily have a causal relationship with this treatment. An AE can therefore be any unfavorable and unintended sign (including a clinically significant abnormal laboratory finding), symptom, or disease temporally associated with the use of an experimental intervention, whether or not related to the intervention.

Progression of the cancer under study or events which are unequivocally due to disease progression should not be reported as an AE during the study (unless it is considered to be drug related by the investigator).

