7.1 Adverse Event Monitoring

Adverse event data collection and reporting, which are required as part of every clinical trial, are done to ensure the safety of subjects enrolled in the studies as well as those who will enroll in future studies using similar agents. Adverse events are reported in a routine manner at scheduled times during a trial. Additionally, certain adverse events must be reported in an expedited manner to allow for optimal monitoring of patient safety and care.

As far as possible, each adverse event should be evaluated to determine:

- duration (start and end dates)
- severity (grade)
- seriousness
- relationship to study agent
- action taken (i.e., none, study agent modification, medical intervention)
- outcome (i.e., resolved without sequelae, resolved with sequelae, ongoing)

Adverse events monitoring begins at the time of initiating study treatment through **90 days** following the last administration of study treatment or study discontinuation/termination, or the initiation of new anti-cancer therapy, whichever is earlier, whether or not related to IPI-549.

Note: Serious adverse events must be recorded in the case report forms for this 90 day-period; however, non-serious adverse events need only be recorded through 28 days post last study drug administration.

All patients experiencing an adverse event at least possibly related to study treatment will be monitored until:

- the adverse event resolves or the symptoms or signs that constitute the adverse event return to baseline;
- any clinically significant abnormal laboratory values have returned to baseline;
- there is a satisfactory explanation other than the study drug for the changes observed; or
- death.

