8.0 AGENT INFORMATION

8.1 Agent IPI-549

Please refer to Investigator's Brochure for more comprehensive information.

Mechanism of action (or Product description):

IPI-549 drug substance is a freebase, white-to-yellow solid. The IPI-549 drug product is formulated in 2 different capsule strengths (5 mg and 30 mg) for oral delivery with excipients (diluent, disintegrant, and lubricant) that are listed in the FDA Inactive Ingredients Database for approved drug products and/or Generally Regarded as Safe.

Availability: Provided by Infinity Pharmaceuticals Inc.

How supplied: IPI-549 is administered as an oral capsule supplied at the dose specified per subject and/or cohort.

Route of administration for this study: IPI-549 should be self-administered orally (approximately every 24 hours). IPI-549 should be swallowed whole with a glass of water (approximately 8 ounces or 240 mL). Subjects must avoid grapefruit and grapefruit juice while on study drug. Subjects should be advised to avoid food and liquids other than water from 2 hours prior to dosing until 1 hour after dosing.

Side effects:

Adverse Reactions Based on Clinical Data

The following side effects have been observed in 12 people who received IPI-549 according to the results from a Phase 1/1b first-in-human, dose escalation study to evaluate the safety tolerability, pharmacokinetics, and pharmacodynamics of IPI-549 monotherapy and in combination with nivolumab in subjects with advanced solid tumors.

Grade 3 or higher TEAEs occurred in 5 (41.7%) subjects (1 each in the 10,15, and 20mg groups and 2 in the 30mg group.) There was 1 occurrence of each of the following Grade 3 or higher TEAEs: anaemia, haematochezia, small intestinal obstruction, pneumonia, lymphocyte count decreased, and malignant neoplasm progression.

Treatment-emergent SAEs occurred in 5 (41.7%) subjects. Each subject had 1 SAE as follows: malignant neoplasm progression (15mg), haematochezia (20mg), peritonitis (20mg), small intestinal obstruction (30mg), and pneumonia (30mg).

The following side effects have been observed in 56 people who received IPI-549.

Blood and lymphatic system disorders:

Anemia

Gastrointestinal Disorders:

Diarrhea

Nausea

Vomiting

Abdominal pain

General disorders and administration site conditions:

Fatigue

Fever

Local swelling

Metabolism and nutrition Disorders:

Hypomagnesaemia

Nervous system disorders:

Headache

Vascular disorders

Hypertension

Skin and subcutaneous tissue disorders:

Rash

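### Hypomagnesaemia is a listed IPI-549 effect, but no scheduled test measures magnesium, so it will be found only incidentally and a low or zero count cannot be read as absence

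*Combined protocol and SAP*

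**What the plan says.** Section 8.1 introduces its longer side-effect list with "The following side effects have been observed in 56 people who received IPI-549". Under metabolism and nutrition disorders the single entry is "Hypomagnesaemia". No count, grade or attribution is given.

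The Schedule of Events has two safety blood tests at every visit, a CBC with differential and a CMP. The CMP row reads "CMP ³ Within 7 days X X X", that is, screening, Day 1, pre-surgery (Day 14) and follow-up. Footnote 3 defines the CMP by listing its 14 analytes: "bicarbonate, calcium, chloride, creatinine, glucose, potassium, sodium BUN, albumin, bilirubin total, alkaline phosphatase, total protein, ALT, AST".

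Section 6.1.6 is the only other text on safety chemistry, and it names no analyte: "Blood chemistry, hematology, and β hCG pregnancy tests will be administered throughout the study to monitor safety". Section 6.2 asks only for laboratory tests at screening.

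Safety and tolerability is a secondary objective (Section 3.2). The matching endpoint in Section 3.3 begins "Adverse events related to IPI-549 (description, grade [CTCAE v5.0], and seriousness". Section 9.5 summarizes adverse events by grade, attribution and system organ class.

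**The concern.** A known effect whose direct evidence is a laboratory value is left without a scheduled laboratory test. Two things follow for the safety objective.

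First, ascertainment is uneven. Anemia, white cell, liver enzyme and bilirubin changes are looked for in every subject at fixed times. Hypomagnesaemia is looked for in no one. Their counts would go into the same summary as if they were comparable, and Section 9.5 has nothing to warn the reader that they are not.

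Second, there is no baseline. Section 6.1.1 treats changes from screening as adverse events. Section 7.1 follows adverse events at least possibly related to treatment, among other end points, until abnormal laboratory values have returned to baseline. A low magnesium found after dosing cannot be shown to be a change and has no baseline to return to. It is also harder to attribute. The trial is single-arm, so no control group helps with attribution, although attribution is part of both the endpoint and the analysis.

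**Working it through.** **1. Coverage of the listed laboratory effects.** The laboratory effects in Section 8.1, set against the scheduled tests:

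| Listed in Section 8.1 | Scheduled test that measures it |
|---|---|
| Anemia | CBC |
| White blood cell count decreased | CBC with differential |
| Increased liver enzymes | CMP (ALT, AST, alkaline phosphatase) |
| Blood bilirubin increased | CMP (total bilirubin) |
| Hypomagnesaemia | None |

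Hypomagnesaemia is the only gap, and no text gives a reason for it. Two sources were not available: the Investigator's Brochure, and the text between Sections 6.1.9.6 and 6.1.11. The latter sits among the research-specimen sections, and the Schedule does not refer to it for safety chemistry.

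**2. Size of the consequence.** The documents give no figure on hypomagnesaemia or its detection, so there is none to reproduce. What follows is an illustration.

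Inputs:
- n = 15, the planned number of subjects (Section 9.2). The safety population could be somewhat larger, because subjects who do not complete two weeks are replaced but still count for safety.
- p, the true rate per subject. This is an assumption. The low end is 1/56, the smallest non-zero count compatible with the effect having been seen among 56 people. 5%, 10% and 20% are added to show a range.
- d, the chance that a case is found. This is also an assumption. d = 1 means that a scheduled test catches every case. Smaller values stand for incidental finding only.

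Formula: P(at least one case found) = 1 − (1 − p·d)^15. Expected number found = 15·p·d.

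With d = 1:
- p = 1/56: 1 − (55/56)^15 = 0.24
- p = 5%: 1 − 0.95^15 = 0.54
- p = 10%: 1 − 0.90^15 = 0.79
- p = 20%: 1 − 0.80^15 = 0.96

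With d = 0.25:
- p = 5%: 1 − 0.9875^15 = 0.17
- p = 10%: 1 − 0.975^15 = 0.32
- p = 20%: 1 − 0.95^15 = 0.54

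| True rate p | Expected true cases (15p) | d = 1 | d = 0.50 | d = 0.25 | d = 0.10 |
|---|---|---|---|---|---|
| 5% | 0.75 | 54% | 32% | 17% | 7% |
| 10% | 1.5 | 79% | 54% | 32% | 14% |
| 20% | 3.0 | 96% | 79% | 54% | 26% |

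**3. Reading a zero.** At a true rate of 10%, the chance of no case found is 1 − 0.79 = 21% with scheduled testing and 1 − 0.32 = 68% if one case in four is found. At 20% the figures are 4% and 46%. A zero from scheduled testing would carry some evidence against a rate of 10% to 20%. A zero from incidental finding would carry little.

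The d = 1 column is an upper limit. It assumes that each case is still present at a draw. Being recorded as a related adverse event would further depend on clinical significance and attribution. Of the four draws, only the pre-surgery one falls at the end of treatment.

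**The case against.** A reader might infer that the trial would report no hypomagnesaemia whatever its true rate. The documents do not support that, because it requires d = 0. Section 7.0 counts as an adverse event "any unfavorable and unintended sign (including a clinically significant abnormal laboratory finding), symptom, or disease temporally associated with the use of an experimental intervention", and does not limit this to scheduled tests. Under Section 7.1, "non-serious adverse events need only be recorded through 28 days post last study drug administration", a window that takes in surgery. Nothing bars an unscheduled magnesium test. A low value found in peri-operative care, or after symptoms, would be recorded.

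A reader might also infer that the grade 3 rule in Section 5.3 could never act on hypomagnesaemia. That fails too. The rule covers any grade 3 toxicity however it is found, and Section 5.3 has subjects monitored continuously. Only cases that are neither symptomatic nor tested escape it.

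Further points on the other side:
- Footnote 3 and Section 8.1 do not contradict each other. One defines a panel, the other lists observed effects, and neither claims that the panel covers the list. This stands: the point is a gap in ascertainment, not an inconsistency.
- The rates are unsourced. This stands. Hypomagnesaemia is also absent from the grade 3 or higher events reported for the first 12 people in Section 8.1. At 1/56, even perfect testing would show a case only 24% of the time.
- Section 9.5 plans no zero row and no statement that the effect is absent. This stands, so a misreading of a zero is a risk and not something the plan provides for.
- The primary endpoint, its power and the stopping rules in Section 9.4 do not rest on magnesium. This also stands, and it limits the weight of the point.

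None of this supplies a scheduled measurement or a baseline value.

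**Conclusion.** The point holds as one of under-ascertainment. Hypomagnesaemia is the only laboratory effect listed in Section 8.1 that the scheduled tests do not measure. As written, the plan would find it only by chance or through symptoms, would probably understate its rate, and would have no baseline for attribution or for the return-to-baseline criterion in Section 7.1.

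The size cannot be fixed from the documents. If one case in four were found incidentally, the chance of seeing any would fall from 54% to 17% at an assumed rate of 5%, from 79% to 32% at 10%, and from 96% to 54% at 20%. Both the rates and the one-in-four figure are assumptions. At the low end of the range little would be seen either way, but a baseline would still be missing.

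This is an inexpensive improvement to a descriptive secondary objective and does not threaten the primary analysis.

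**What to change.** Add magnesium to the analytes in footnote 3, at least at baseline and at the pre-surgery visit, and preferably also at Day 1 and follow-up. Baseline and pre-surgery give the within-subject comparison that attribution needs. The cost is one analyte on blood already drawn, with no new visit or procedure. It leaves dose, treatment and stopping rules unchanged.

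If magnesium is not added, put one sentence in Section 9.5: hypomagnesaemia is not systematically ascertained in this trial, and a low or zero count will not be interpreted as absence of the effect. That costs nothing, but it leaves the missing baseline as it is.
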